7.4.2 Exclusion criteria

- Lack of compliance with any inclusion criteria
- CI user with contralateral hearing equal to or better than 60 dB (PTA measured at 500, 1000, and 2000Hz))
- EAS user (user of an EAS audio processor)
- Implanted with C40X and C40C
- Implanted with an ABI or Split electrode array
- Known allergic reactions to components of the investigational medical device
- Unstable psychological status
- Anything that, in the opinion of the Investigator, would place the subject at increased risk or preclude the subject's full compliance with or completion of the study

7.5 Randomization and Blinding

The order of the audio processor testing will be randomised for each subject and study visit. Additionally, it will be randomised which audio processor configurations will be taken home after a particular visit. These randomizations will be performed to avoid any sequence-effects (e.g. training effect, fatigue effect). The particular fitting configuration and the order of the test procedures is verbally stated in the respective CRFs for each subject and each study visit.

Details on randomization can be found in the Data Management Plan (DMP).

7.6 Tests / Study Variables

Audio Processor	Configuration	Visit 1	Visit 2 ¹	Visit 3 ¹	Visit 4 ¹	Visit 5 ¹
		Speech in quiet (S0)	Speech in noise (SON0 & SON0T0)	Speech in noise (S0 ± N45 ± N35)	Subjective ratings	Subjective ratings
SONNET	Default SONNET	✓			✗	✗
SONNET 2	OPUS 2	✓	✓	✓	✓	✓
SONNET 2	Default SONNET	✓	✓	✓	✓	✓
SONNET 2	SONNET 2/ Configuration 1 ²	✓	✓	✓	✓	✓
SONNET 2	SONNET 2	✓	✓	✓	✓	✓
SONNET 2	Configuration 2 ²	✓	✓	✓	✓	✓
SONNET 2	SONNET 2	✓	✓	✓	✗	✗
SONNET 2	Configuration 3 ²	✓	✓	✓	✗	✗
SONNET 2	SONNET 2/ Configuration 4 ²	✓	✓	✓	✗	✗
Questionnaires	SONNET: APSQ HISQUI SSQ	SONNET: SONNET 2 ³ Questionnaire HISQUI SSQ	SONNET 2: SONNET 2 ³ Questionnaire APSQ HISQUI SSQ	SONNET 2: SONNET 2 ³ Questionnaire HISQUI SSQ	SONNET 2: SONNET 2 ³ Questionnaire HISQUI SSQ	SONNET 2: SONNET 2 ³ Questionnaire HISQUI SSQ

¹ Study Visit is conducted 2 weeks (± 1 week) after the previous visit

² Details on all SONNET 2 configurations are described in the CIP

³ The questionnaire will be completed for the SONNET 2 in the SONNET default configuration and one of the four SONNET 2 configurations (which will be randomised across subjects).

7.6.1 Speech testing in quiet

The Freiburg Monosyllabic Word test evaluates the number of correctly repeated words in % correct at a fixed presentation level.

7.6.2 Speech testing in noise

The OLSA test is used to assess the speech-recognition threshold for 80% correct word recognition in noise (SRT80 in dB SNR). The noise level is fixed, and the speech level is adaptive.

7.6.3 Subjective ratings

7.6.3.1 Subjective sound

Subjective sound quality ratings of the different SONNET 2 configurations will be assessed on a visual analogue scale (VAS) for a range of signals comprising different samples of speech, music, and background noises. The subject will rate the perceived quality on different scales compared to a reference condition.

7.6.3.2 ACALES Test

In this test, the subject will listen to speech in noise and will rate the subjectively perceived listening effort on a scale from "effortless" to "extremely effortful". Depending on the rating of the subject, the level of the speaker will be varied adaptively while the noise level is kept constant. This test will be performed in different fitting configurations and test set-ups

7.6.4 Questionnaires

7.6.4.1 Audio Processor Satisfaction Questionnaire (APSQ)

The APSQ is a validated general questionnaire which is designed to assess the handling of MED-EL devices. It assesses the wearing comfort, sound quality, and other device-specific factors related to the audio processor with 15 items on a VAS scale from 0 ('does not agree at all') to 10 ('fully agrees'). If an item does not apply to the subject, then the subject can tick the 'not applicable' option. The maximum number of incomplete answers for the validation analyses is set at three items per subject; if this number exceeds, then the subject shall be excluded.

7.6.4.2 Hearing Implant Sound Quality Index 19 (HISQUI19)

The questionnaire consists of 19 seven-level Likert items ranging from 'always = 7' to 'never =1'. Added percentage values support the answering of the items. The total score is the sum of all items and ranges from 19 to 133 points. Missing data and the answer option 'not applicable' (N/A) are treated as 'missing values'. The maximum number of incomplete answers are set at three items per subject; if this number exceeds the subject shall be excluded.

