3 GOALS OF THE SAP

The SAP is intended to be a comprehensive and detailed description of the methods and presentation of data analysis proposed for a clinical investigation, to avoid post hoc decisions that may affect the interpretation of the statistical analysis.

The SAP is intended to be a comprehensive and detailed description of the methods and presentation of data analysis proposed for a clinical investigation, to avoid post hoc decisions that may affect the interpretation of the statistical analysis.

The SAP is intended to be a comprehensive and detailed description of the methods and presentation of data analysis proposed for a clinical investigation, to avoid post hoc decisions that may affect the interpretation of the statistical analysis.

The SAP is intended to be a comprehensive and detailed description of the methods and presentation of data analysis proposed for a clinical investigation, to avoid post hoc decisions that may affect the interpretation of the statistical analysis.

The SAP is intended to be a comprehensive and detailed description of the methods and presentation of data analysis proposed for a clinical investigation, to avoid post hoc decisions that may affect the interpretation of the statistical analysis.

The SAP is intended to be a comprehensive and detailed description of the methods and presentation of data analysis proposed for a clinical investigation, to avoid post hoc decisions that may affect the interpretation of the statistical analysis.

The SAP is intended to be a comprehensive and detailed description of the methods and presentation of data analysis proposed for a clinical investigation, to avoid post hoc decisions that may affect the interpretation of the statistical analysis.

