7.6.4.3 SSQ12 (Speech Spatial Qualities) in German

The SSQ questionnaire (Noble et al. 2013) is a sensitive and specific measure to assess the impact of hearing loss on speech perception, sound localization, and QoL. The SSQ12 consists of 12 questions that the subjects score on a scale from 0 (not at all) to 10 (perfectly). The total score is the sum of all items and can range between 0 and 120. The items can also be classified into the following subscores:

- ◆ Speech: Items 1 - 5
- ◆ Spatial: Items 6 – 8
- ◆ Qualities: Items 9 – 12

Scoring rules:

- ◆ Questions answered with "not applicable" (N/A) or not answered are rated as missing value.
- ◆ The maximum number of incomplete answers will be set at 2 items per subject; if this number exceeds the subject will be excluded.
- ◆ The results of the questions can be added up totally or within the subgroups listed above.

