12.2 Handling of Missing Data

Missing data will be treated as missing values.

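### HISQUI19 and SSQ12 totals are defined as plain sums while incomplete forms are kept, and no rule scales the total for missing items

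*SAP*

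**What the plan says.** For HISQUI19 (SAP 7.6.4.2) there are 19 items scored 1 to 7. "The total score is the sum of all items and ranges from 19 to 133 points". Blank and not-applicable answers are both handled as missing. On how many are allowed: "The maximum number of incomplete answers are set at three items per subject; if this number exceeds the subject shall be excluded".

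For SSQ12 (SAP 7.6.4.3) there are 12 items scored 0 to 10. "The total score is the sum of all items and can range between 0 and 120". Not-applicable and unanswered items are again missing. The limit is lower: "The maximum number of incomplete answers will be set at 2 items per subject; if this number exceeds the subject will be excluded". The scoring list ends with the only operation it names: "The results of the questions can be added up totally or within the subgroups listed above".

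The general rule in SAP 12.2, repeated in Protocol 15.3, is "Missing data will be treated as missing values". The conversion formula mentioned in Protocol 10.2.4.3 links the short and full versions of the SSQ and does not deal with missing items. SAP section 3 says the plan is meant "to avoid post hoc decisions that may affect the interpretation of the statistical analysis".

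**The concern.** The total is defined for a complete form, but the plan also keeps incomplete forms. Between the two there is no statement of how a total is formed from 16 to 18 HISQUI19 items or from 10 or 11 SSQ12 items. An analyst who follows the text will add what was answered, because nothing else is named. Totals built on different numbers of items are then not on the same scale.

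This matters because the totals are compared within subjects. Protocol 15.1.2.2 allows significance tests between test intervals where a total score exists, and SAP 11.2.2 names the paired t-test and the Wilcoxon signed-rank test. A subject who marks one item as not applicable at one visit and answers it at another shows a change that is partly or wholly an effect of scoring. If the analyst prorates instead, that choice is made after the incomplete forms have been seen, which SAP section 3 sets out to prevent.

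**Working it through.** **Inputs.** HISQUI19: 19 items, 1 to 7, at most 3 missing (SAP 7.6.4.2). SSQ12: 12 items, 0 to 10, at most 2 missing; the Spatial subscore has 3 items (SAP 7.6.4.3).

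**1. The plan's own ranges.** HISQUI19: 19 × 1 = 19 and 19 × 7 = 133. SSQ12: 12 × 0 = 0 and 12 × 10 = 120. Both stated ranges reproduce, but only with every item answered.

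**2. Ranges when answered items are added and the maximum is missing.**
- HISQUI19: 16 × 1 = 16 to 16 × 7 = 112. The lower end is below the stated 19.
- SSQ12: 0 to 10 × 10 = 100. The stated 120 cannot be reached.

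**3. Shortfall against a prorated total.** With k of n items answered and mean answered score a, the plain sum is k·a and the prorated total is n·a. The relative shortfall is (n − k)/n.

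| Scale | 1 missing | Maximum missing |
|---|---|---|
| HISQUI19 | 1/19 = 5.3% | 3/19 = 15.8% |
| SSQ12 | 1/12 = 8.3% | 2/12 = 16.7% |

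**4. Effect on a within-subject change.**
- *Unequal missing counts.* Each extra missing item removes about one item mean. The scale midpoints are (1 + 7)/2 = 4 and (0 + 10)/2 = 5, so a one-item difference shifts the change by about 4 points (HISQUI19) or 5 points (SSQ12). As an example, take a subject who scores 5 on every answered HISQUI19 item at both visits, with no item missing at one visit and 3 missing at the other. The plain sums are 95 and 80, an apparent change of 15 points with no real change. Both prorated totals are 95.
- *Equal missing counts.* If m items are missing at both visits and every item truly changes by d, the plain sum changes by (n − m)·d, not n·d. The change shrinks by m/n, at most 15.8% or 16.7%.

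**5. Average shrinkage under an assumed rate.** The documents give no rate of not-applicable or blank answers. Assume 2% to 10% per item, items independent, the rate equal at both visits, and forms over the limit dropped. The missing count then follows a binomial distribution truncated at 3 or 2, and the mean shrinkage is E(M)/n.

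| Assumed rate | HISQUI19 | SSQ12 |
|---|---|---|
| 2% | 0.378/19 = 2.0% | 0.236/12 = 2.0% |
| 5% | 0.907/19 = 4.8% | 0.550/12 = 4.6% |
| 10% | 1.575/19 = 8.3% | 0.941/12 = 7.8% |

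Equal rates at both visits therefore do not remove the error when there is a true change.

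**6. Subscores.** Two missing items are within the SSQ12 limit even if both are Spatial items. That subscore would then rest on one item, with a maximum of 10 out of 30.

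**The case against.** The strongest reply is about consequence. SAP 9.2 calls the secondary analyses exploratory and formulates no hypotheses for them, and Protocol 15.1.2.2 plans tests only where applicable. The primary OLSA analysis does not use these scales. All of this stands, and it limits the severity.

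SSQ12 is also the weaker case. Its scoring list can be read as an instruction to add the answered items, and a sum of 0 to 100 lies inside 0 to 120, so nothing there is contradicted. Only HISQUI19 conflicts with its own stated range. The comparability problem nevertheless applies to both scales.

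A rule may also exist elsewhere. Protocol 14.5 and SAP 15 refer to the Data Management Plan, and the protocol cites publications on both instruments. None of these is available here. Still, the SAP sets out its own scoring and does not refer elsewhere for this step.

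Three stronger readings are tempting, and the documents do not support them.
- *Any missing item voids the total.* The stated tolerances imply that incomplete forms are used, since they would otherwise have no effect on the total.
- *The limit accumulates over all visits, so one item that never applies would exclude a subject.* The limits are worded per subject, and the SAP 7.6 table shows "Questionnaire HISQUI SSQ" in its visit columns. But each limit sits in the description of a single form, and an item left blank repeatedly is still one item. Protocol 10.2.4.2 and 10.2.4.3 also place these questionnaires at the first and third visits only. On that schedule the count would be 2, which exceeds neither limit.
- *The group comparisons are shown to be biased by a known amount.* Without a rate of not-applicable answers, no group-level figure can be given. Without a standard deviation of change, no effect on the tests can be stated.

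**Conclusion.** The point holds as a minor defect. The only scoring operation the SAP names does not fit the incomplete forms it keeps. The limits on individual forms (15.8% and 16.7%) and the HISQUI19 minimum of 16 follow from the SAP's own numbers. The shift of 4 or 5 points assumes item means at the scale midpoint. The average shrinkage of about 2% to 8% rests on the assumed rate of 2% to 10% and is illustrative only. Confidence is medium, because the Data Management Plan was not available.

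**What to change.** Add one or two sentences to each of SAP 7.6.4.2 and 7.6.4.3 before analysis:

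- HISQUI19 total = mean of answered items × 19 when at most 3 items are missing.
- SSQ12 total = mean of answered items × 12 when at most 2 items are missing.
- Apply the limit to each questionnaire administration. If it is exceeded, set only that administration's total to missing and keep the subject's other data.

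This restores the stated ranges for every scored form: 19 × (1 to 7) = 19 to 133, and 12 × (0 to 10) = 0 to 120. If SSQ12 subscores are to be reported, their handling of missing items should be stated too. If the Data Management Plan already holds a rule, cite it in the SAP.

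No new data are needed. The downside is that prorating assumes unanswered items resemble the answered ones, which may not be true of items marked not applicable.

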7.6.4.3 SSQ12 (Speech Spatial Qualities) in German

The SSQ questionnaire (Noble et al. 2013) is a sensitive and specific measure to assess the impact of hearing loss on speech perception, sound localization, and QoL. The SSQ12 consists of 12 questions that the subjects score on a scale from 0 (not at all) to 10 (perfectly). The total score is the sum of all items and can range between 0 and 120. The items can also be classified into the following subscores:

- ◆ Speech: Items 1 - 5
- ◆ Spatial: Items 6 – 8
- ◆ Qualities: Items 9 – 12

Scoring rules:

- ◆ Questions answered with "not applicable" (N/A) or not answered are rated as missing value.
- ◆ The maximum number of incomplete answers will be set at 2 items per subject; if this number exceeds the subject will be excluded.
- ◆ The results of the questions can be added up totally or within the subgroups listed above.

7.6.4.4 SONNET 2 questionnaire

A study specific questionnaire was developed to compare the four new SONNET 2 fitting configurations to the previous SONNET settings. The questionnaire covers different everyday situations (e.g. conversations in a cocktail party setting, speech different background noise situations, music etc.). The subjects are asked to state which fitting configuration they prefer and to give a reason why. Additionally, there are blank spaces where each subject can state situations which are important to them, they can state their preferred fitting and also tick why a particular fitting was preferred. Missing data are treated as missing values.

8 SAMPLE SIZE

The primary objective of this study is to show non-inferiority of SONNET2 in a OLSA in noise speech test (S0N0) compared to the SONNET. The margin of non-inferiority is set to 2 dB SNR.

Comparable data of the final report "Performance of Cochlear Implant Patients with Microphone Directionality and Wind Noise Reduction with the "SONNET" of the OLSA in noise speech test (S0N0) were used as basis for the sample size calculation:

OPUS2	mean: 0.589 dB;	± SD: 1.586 dB vs.
SONNET natural-MILD	mean: -0.088 dB;	± SD: 1.463 dB

The sample size was estimated using the formula on noninferiority (Chow, Shao et al. 2008):

$$N = (1 + \frac{1}{r})(\sigma \frac{Z_{crit} + Z_{pwr}}{(\mu_A - \mu_B) - \Delta})^2$$

Assuming a non-inferiority margin of 2 dB (Δ), with an alpha-level of 0.025 (noninferiority, one-sided) and a power of 90%, a minimum sample size of 13 subjects was calculated (Z_{crit} is the normal quantile for the 0.025 alpha level, and Z_{pwr} is the normal quantile for the 90% power). To allow for possible dropouts (approximately 20%) and to provide additional safety and efficacy data, a maximum of 30 subjects will be included in this study.

9 HYPOTHESES

9.1 Hypothesis for the Primary Objective

The primary objective of this study is to show non-inferiority of SONNET2 in a OLSA in noise speech test (S0N0) compared to the SONNET. The margin of non-inferiority is set to 2 dB SNR.

- Verbal formulation

Hypothesis H₀ (Null Hypothesis):

Speech perception with the SONNET 2 in its default setting in the OLSA in noise (S0N0) is inferior to the speech perception in the same test condition with the SONNET. A mean difference of ≥ 2 dB is considered as a clinically relevant difference.

Hypothesis H₁ (Alternative Hypothesis):

Speech perception with the SONNET 2 in its default setting in the OLSA in noise (S0N0) is non-inferior to the speech perception in the same test condition with the SONNET. A mean difference of less than 2 dB is not considered as a clinically relevant difference.

- Mathematical formulation

$$H_0: \mu_1 - \mu_2 \geq \Delta \text{ (2 dB SNR)}$$

$$H_1: \mu_1 - \mu_2 < \Delta \text{ (2 dB SNR)}$$

Where: μ_1 = mean OLSA in noise (S0N0) results as dB SNR with the SONNET

μ_2 = mean OLSA in noise (S0N0) results as dB SNR with the SONNET2

9.2 Hypotheses for the Secondary Objectives

The secondary objectives of this study are to provide additional evidence on the performance of SONNET 2-specific front-end features. Thus, the analyses are of an explorative nature and will not influence the results of the primary outcome of the study. Due to the exploratory nature of the secondary objectives, no hypotheses are formulated a priori.

10 GENERAL CONSIDERATIONS

10.1 Timing of Analyses

The final analysis will be performed when all enrolled subjects have finished the last study visit. No interim analysis is planned.

10.2 Analysis Population

The Per Protocol Analysis (PP) will include all patients who adhere to the major criteria of the protocol; otherwise that patient will be excluded from the analysis.

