4.6 Study population

This study aims to enrol experienced adult users of the MED-EL cochlear implant system.

- **Target population:** adults of both sexes suffering from sensorineural hearing loss as specified in the SONNET 2 Intended Use (IU) in the User Manual (See Section 21.1, Appendix 1 for details)
- **Accessible population:** target population matching all inclusion and exclusion criteria as defined in section 8.1
- **Intended population:** accessible population that can be recruited by the study site appointed for this study
- **Actual population:** intended population enrolled in the study without considering drop-out or withdrawal
- **Analytic population:** actual population meeting all criteria for analysis

the study population is identified with the analytic population.

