8.5 Early Withdrawal

8.5.1 Reason for Early Withdrawal

The Investigator may decide to withdraw a subject from the study for one of the following reasons upon agreement with MED-EL:

- Health issues (e.g. occurrence of SAEs, subject's death, etc.)
- Further participation would cause an unacceptable risk to the subject
- The subject moved away
- The subject does not comply with the CIP (e.g. s/he does not attend the visits on schedule; she/he does not communicate relevant medical issues to the Investigator, etc.)

In accordance with the Declaration of Helsinki (Fortaleza, 2013), subjects are free to terminate their participation in the study at any time for any or for no reason, without prejudicing their basic right to receive the best treatment available for them.

If a subject decides to withdraw early, he/she must return the SONNET 2 audio processor.

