7 STUDY METHODS

7.1 Type of Study / Study Design

This study has been planned as a mono-centric, open label, prospective longitudinal study where each subject acts as his/her own control.

The SONNET 2 is an incremental innovation to the SONNET audio processor with additional front-end processing features which are designed to improve patient performance in specific auditory environments. The study is designed to prospectively follow-up experienced SONNET users who received the SONNET 2. As intra-individual control, subjects will be acutely tested with the SONNET in the same test conditions as with the SONNET 2.

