13 PROTOCOL DEVIATIONS

Protocol deviations that could impact the statistical analysis shall be discussed with the Clinical Research Manager as well as with the Study Monitor and the Data Manager. If applicable, the methods used to analyse them shall be specified and reported in the "Final Study Report".

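### Per protocol is the only analysis set and its exclusion criteria are unlisted, so a complete Visit 2 primary pair may be dropped with no analysis of all complete pairs beside it

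*SAP*

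**What the plan says.** SAP 10.2 defines a single set, per protocol. It covers patients who keep to the protocol's major criteria; "otherwise that patient will be excluded from the analysis". The SAP does not say which criteria are major.

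Protocol 4.6 also leads to one set. The analytic population is the "actual population meeting all criteria for analysis", and "the study population is identified with the analytic population". Those criteria are not listed either. Section 4.6 does name an actual population of all enrolled subjects, but no analysis is assigned to it.

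SAP 11.2.1 sets the 95% confidence interval for the mean S0N0 difference against the 2 dB margin and names no other set. SAP 12.2 gives missing data one sentence, and neither document contains a sensitivity analysis.

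On deviations, SAP 13 says: "Protocol deviations that could impact the statistical analysis shall be discussed with the Clinical Research Manager as well as with the Study Monitor". It gives the Data Manager a part in that discussion too. Methods for analysing them are to be specified and reported in the final report where applicable. SAP 7.1 describes the study as "mono-centric, open label, prospective longitudinal study where each subject acts as his/her own control".

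**The concern.** Protocol 9.2 places all S0N0 testing, with the SONNET and with every SONNET 2 set-up, at Visit 2. Protocol 9.3 to 9.5 then add three visits, each with a window of one week either side. A late or missed Visit 4 says nothing about the validity of the Visit 2 thresholds, yet the plan leaves room to remove that subject from the primary analysis.

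Random exclusions would cost only precision. Selective ones would bias the estimate, and the protocol offers a plausible route to selection. Subjects know which processor they wear, and their own SONNET stays at the clinic until they finish or withdraw (Protocol 4.3 and 9.6). Someone unhappy with SONNET 2 gets the familiar processor back sooner by leaving. Someone content with it has a reason to finish, because completers may keep it. If those who leave or deviate also have worse SONNET 2 thresholds, a set restricted to adherent subjects makes SONNET 2 look better than it is.

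**Working it through.** **Inputs.** From SAP 8 and Protocol 7.3: SDs 1.586 and 1.463 dB, margin 2 dB, one-sided alpha 0.025, power 90%, minimum 13 subjects, dropout allowance about 20%, maximum 30 subjects. The documents do not give the true difference, the within-subject correlation, the share of complete pairs that would be excluded, or how excluded subjects would differ. These are assumed below, with ranges.

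**The plan's own figure.** Pooled SD = √((1.586² + 1.463²)/2) = 1.526. With r = 1 and true difference 0, N = 2 × (1.526 × (1.960 + 1.282)/2)² = 12.23, rounded up to 13. The stated minimum reproduces, so this point does not concern the sample size.

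**Precision.** SD of the paired difference = √(1.586² + 1.463² − 2ρ × 1.586 × 1.463), which is 1.528 dB at ρ = 0.5. Half-width = t(0.975, n−1) × SD/√n.

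| Assumed ρ | SD of difference | n = 30 | n = 24 |
|---|---|---|---|
| 0 | 2.158 | 0.81 dB | 0.91 dB |
| 0.5 | 1.528 | 0.57 dB | 0.65 dB |
| 0.8 | 0.971 | 0.36 dB | 0.41 dB |

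Going from 30 to 24 pairs widens the interval by about 13%. With 24 pairs and true difference 0, power is still at least 99% at every ρ in the table.

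**Bias.** Take the difference as SONNET 2 minus SONNET; a higher SRT is worse. If a fraction f of pairs is excluded and those subjects are on average e dB worse than those kept, the mean in all pairs equals the mean in those kept plus f × e.

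- f = 0.2, e = 1.5 dB: shift = 0.3 dB, or 15% of the margin.
- 2 of 24 excluded, e = 1, 2, 3 dB: shift = 0.08, 0.17, 0.25 dB.
- 6 of 30 excluded, e = 1, 2, 3 dB: shift = 0.20, 0.40, 0.60 dB.

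**Effect on the conclusion.** If the 24 kept subjects show a mean difference of 0, the upper limit is 0.65 dB at ρ = 0.5. Adding back 0.3 dB gives 0.95 dB. At ρ = 0 with the largest shift, 0.91 + 0.60 = 1.51 dB. All are below 2 dB. Holding the half-width at 0.65 dB, a 0.3 dB shift reverses the conclusion only if the per-protocol estimate lies between 2 − 0.65 − 0.3 = 1.05 dB and 2 − 0.65 = 1.35 dB.

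**Worst-case bound.** In 100,000 simulated trials with normal differences and the true difference at the 2 dB margin, the subjects with the largest differences were removed and the paired t limit recomputed. With 24 pairs the one-sided error goes from about 0.025 to 0.07, 0.14 and 0.24 after one, two and three removals. With 30 pairs it goes to 0.07, 0.13 and 0.21. This is a ceiling, because it assumes exclusion picks out exactly the worst differences.

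**The case against.** A per-protocol set is not in itself wrong for non-inferiority. Each subject is his or her own control and both thresholds come from the same visit, so selection would have to act on the within-subject difference and not just on general ability. Protocol 8.7 lets enrolment continue until the minimum is reached in the analytic population, which protects precision. All of this stands and limits the size of the problem. None of it supplies the missing comparison.

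A reader might infer several stronger things that the documents do not support.

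- **That exclusions are decided after all visits.** SAP 10.1 says "The final analysis will be performed when all enrolled subjects have finished the last study visit". That times the analysis, not the classification of subjects, and Protocol 7.5 has sites report deviations to the Monitor immediately. The timing of classification is simply unstated.
- **That withdrawal or a later deviation discards the Visit 2 data.** Protocol 8.5.1 lists "The subject does not comply with the CIP" among the reasons for which the investigator may withdraw a subject. It does not say that data already collected are removed, and nothing says that a late Visit 4 or 5 breaches a major criterion.
- **That exclusions would be invisible.** Protocol 7.5 lists relevant deviations in the final report, Protocol 8.5.2 records withdrawals and seeks reasons, and SAP 13 reports on deviations where applicable. A reader would see that exclusions occurred, but not what they did to the estimate.
- **That 20% of complete pairs will be lost.** The 20% in SAP 8 is a dropout allowance. It is used above only as an illustration, and subjects lost before Visit 2 have no pair to recover.
- **That the bias favours the hypothesis as printed.** SAP 9.1 writes the difference as SONNET minus SONNET 2. In that direction, removing poor SONNET 2 performers raises the difference, away from the printed alternative. The bias toward non-inferiority holds for SONNET 2 minus SONNET.
- **That the SAP breaches ICH E9.** SAP 2 says its recommendations are incorporated, but neither document sets out what they require on analysis sets. The point does not rely on it.

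**Conclusion.** The point holds as a permitted weakness, not a certain loss. The only analysis set depends on unlisted criteria, the study is open label, no rule fixes classification before results are seen, and no analysis of all complete pairs would show what exclusions did to the primary estimate. That sits poorly with the aim in SAP 3 of avoiding post hoc decisions.

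The practical effect is probably modest. With a true difference near 0, the interval stays well inside 2 dB across the assumed correlations and shifts. It would matter if the result fell near the margin, where a few selective exclusions among 24 to 30 pairs could change the conclusion. The 0.3 dB shift rests on two assumed values and the half-widths on an assumed correlation. This is a cheap improvement, not a flaw that invalidates the design.

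**What to change.** - Analyse the primary contrast in all enrolled subjects with both Visit 2 S0N0 SRTs, whatever happens afterwards. Report the per-protocol result beside it.
- List in SAP 10.2 the deviations that lead to per-protocol exclusion, and classify every subject before the S0N0 results are analysed.
- Report each exclusion with its reason, and count separately any enrolled subject who has no complete Visit 2 pair.
- Claim non-inferiority only if the upper 95% confidence limit of SONNET 2 minus SONNET is below 2 dB in each set. State that direction, and that a higher SRT is worse.

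The cost is a paragraph of SAP text and one more run of the same analysis. No extra visits, data or subjects are needed: the minimum stays 13, and 13/(1 − 0.20) = 16.25, rounded up to 17, is under the maximum of 30. The small downside is that the claim must hold in both sets.
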